**4.4 Concomitant Medications and Post Study Treatment**

#### **4.4.1 General Instructions on Study Treatment**

Other medications may be given if the Investigator considers they are essential for subjects' safety and health. All medications taken by subjects must be recorded on eCRF.

From the ICF signed date to one week after treatment completion (Visit 16), any concomitant medications (study medications and other medications) or the changes on dosages of previous medications must be documented in the corresponding eCRF section. Reasons for giving the medications, administration dates (start and stop dates), and dosage information (dose, route, frequency) should also be documented.

#### **4.4.2 Prohibited and Restricted Medications**

Other antidiabetic drugs, except the study medications, are not allowed from the single-blind placebo run-in period throughout the study. If hyperglycemia occurs and the withdrawal criterion for hyperglycemia is met, the subject will be discontinued from the study. The medications for AE treatment or the medications which have been in continuous use before the study are not considered as prohibited and restricted medications.

Unless emergency, subjects are not allowed to take any new medications which have not been used at screening, or adjust current dosage of any study medication or concomitant medications without permission from the Investigator. In case of any emergency when there is any clinical indication needing additional medications or dosage change of concurrent medications, the subjects must inform the Investigator within reasonable timeframe before concomitant medications are started. The information, including drug name, dosage, route of administration, treatment purpose and administration dates are confirmed and recorded by the Investigator.

#### **The following medications are strictly prohibited unless for special medical condition**

- Any antidiabetic drug (including traditional Chinese medicine) other than the study medications (starting from the run-in period)
- Hypoglycemic healthcare product
- Oral or injectable glucocorticoid
- Any known potent or moderate liver enzyme CYP450 3A4/5 inducers/inhibitors, including but not limited to:

Potent liver enzyme inducers: barbitals (especially phenobarbital), carbamazepine, diphenylhydantoin sodium, rifampin, dexamethasone, etc.

Potent liver enzyme inhibitors: ketoconazole, itraconazole, voriconazole, posaconazole, clarithromycin, indinavir, ritonavir, saquinavir, telithromycin, Boceprevir, nelfinavir, Telaprevir, conivaptan, nefazodone.

- Any unauthorized drugs (i.e., investigational drugs not marketed yet).

#### **4.4.3 Contraception**

From screening to 1 month after the last dose of study medications, female subjects with childbearing potential must use high-efficiency, medically approved contraception methods (e.g. barrier type intrauterine device combined with spermicides, IUD implanted at least 3 months before study, oral contraceptives and preventive measures). The same method is recommended to be used throughout the study.

If a female subject finds menstruation is delayed, she should contact the Investigator as soon as possible for a blood pregnancy test. Study medications must be discontinued immediately once the blood pregnancy test is positive. See Section 7.12 in the protocol for procedures for handling pregnancy.

#### **4.4.4 Diet Control and Exercise Intervention**

Instructions are given to subjects on nutrition and physical exercise, how to identify the signs and symptoms of hypoglycemia and hyperglycemia, and how to use blood glucose meter (refer to Appendix 4). The Investigator should ask subjects to keep fasting for at least 8 hours before each visit to study sites (from Visit 3 to Visit 15). Each site is suggested to give subjects instructions on nutrition and diet and ask them to follow the standard diet guideline for diabetes patients (refer to Appendix 8).

#### **4.4.5 Post Study Treatment**

After 52-week treatment is completed, the investigational drug (HMS5552 tablets) is stopped and subjects proceed to 1-week safety observation period. In the safety observation period, in principle, no antidiabetic drugs can be used until the Visit 16 telephone follow-up is completed. Routine treatment can be initiated after Visit 16.

Subjects can contact the Investigator if any hyperglycemia or discomfort occurs between Visits 15 and 16. Depending on disease status, the Investigator decides whether to conduct the telephone follow-up in advance. Under special medical conditions, subjects can take routine antidiabetic treatment in advance for safety consideration. The reasons need to be recorded on eCRF.

### **4.5 Discontinuation of Study Treatment, Withdrawal, or Termination of Study**

During the study, the Investigator should make every effort to encourage subjects to complete the entire study.

Subjects have the right to withdraw from the study treatment for any reason and at any time. The Investigator has the right to require subjects to discontinue the study treatment or withdraw from the study.

In addition, the reasons for discontinuation of study treatment or withdrawal from the study include but not limited to:

- Withdrawal of informed consent form by subjects
- AEs
- Hyperglycemia
- Hypoglycemia
- Pregnancy
- Subjects do not comply with study treatment or scheduled visits (e.g., drug administration or visits not following Investigator's instructions)
- Major protocol deviations and high risks to subjects as considered by the Investigator
- Lost to follow-up
- Others.

Subject withdrawal occurring before randomization for any reason (e.g., not meeting the inclusion criteria) is considered as “screening failure”.

The Sponsor can terminate the study or certain study site based on the overall consideration for the study.

Specific early withdrawal criteria due to hypoglycemia, hyperglycemia, and abnormal liver function have been defined to ensure subject safety. See Sections 4.5.1 to 4.5.3.

Subjects who expect to re-enter the study after discontinuation of study treatment is allowed if the interval is  $\leq$  2 weeks since discontinuation, which will be decided by the Investigator after consultation with the Sponsor.

### **32.5.1 Withdrawal Due to Hypoglycemia**

#### **4.5.1.1 Definition of Hypoglycemia**

Hypoglycemic events are collected and classified as follows according to the China guidelines for the prevention and treatment of T2DM (2013), the Clinical Trials Guidelines for Diabetes Therapeutic Drugs and Biological Products (2012), and a joint statement made by the American Diabetes Association (ADA) and the European Association for the Study of Diabetes (EASD) recently published in November 2016 for identifying and reporting hypoglycemic events:

1. Fingertip or venous plasma glucose value  $\geq 3.0 \text{ mmol/L}$  and  $\leq 3.9 \text{ mmol/L}$ , with or

without symptoms of hypoglycemia;

2. Fingertip or venous plasma glucose value < **3.0 mmol/L**, with or without symptoms of hypoglycemia;
3. **Severe hypoglycemia**: assistance from others is needed, usually with disturbance of consciousness, and neurological symptoms improve significantly or disappear after correction of hypoglycemia.

Hypoglycemia symptoms may include shakiness, hot flashes, vertigo, weakness, cold limbs, anxiety, dizziness, hunger, palpitations, and blurred vision, etc..

In addition, based on The Clinical Trials Guidelines of Diabetes Treatment Drug and Biological Products (2012), the following possible hypoglycemic events are also collected but will not be used for hypoglycemia assessment:

Possible symptomatic hypoglycemia: presenting with hypoglycemia symptoms, but without plasma glucose test results;

Relative hypoglycemia: presenting with hypoglycemia symptoms, but with plasma glucose > 3.9 mmol/L (fingertip or venous).

#### **4.5.1.2 Rules for Withdrawal due to Hypoglycemia**

1. If severe hypoglycemia occurs (help from others is needed, usually with disturbance of consciousness, and neurological symptoms improve significantly or disappear after correction of hypoglycemia) and no other reason (e.g., physical exercise increase or meals skipping) except for the study medications can be found, the study medications are discontinued and the subjects withdraw from the study.
2. If fingertip or venous plasma glucose value is < 3.0 mmol/L and the result occurs twice at two consecutive visits without other reasons (e.g., physical exercise increase or meals skipping) except for the study medications, the study medications are discontinued and the subjects withdraw from the study.

#### **Subjects should be informed to contact study sites in following conditions:**

Any hypoglycemia that needs help (i.e., severe hypoglycemia), or any occurrence of hypoglycemia with fingertip or venous plasma glucose value  $\leq$  3.9 mmol/L.

Notes: As noted before, subjects record all symptoms related to hypoglycemia and fingertip plasma glucose values in subject diaries. The Investigator should review each hypoglycemia event and carefully inquire about the associated symptoms, treatment, and duration etc. Hypoglycemia documented in subject diaries needs to be confirmed by reviewing glucose meter records. All hypoglycemic events confirmed by the Investigator must be recorded on the hypoglycemia review form in eCRF.

#### 4.5.2 Withdrawal due to Hyperglycemia

Between Visits 2 and 15, subjects should carry out SMBG according to SMBG guidance (refer to Appendix 4 for procedures of SMBG). Subjects should contact the Investigator timely if plasma glucose exceed the value specified in SMBG guidance. Depending on the fingertip plasma glucose values, diet and exercise condition, the Investigator determines whether the subjects should return to study sites in advance for laboratory tests.

If a subject has a FPG value reaching the following criteria twice (at least once tested in the central laboratory) without any apparent causes at two consecutive visits, the Investigator will evaluate whether the subject will withdraw from the study with the reason recorded as hyperglycemia based on subject's actual situation.

1. Day 1–before Week 12: venous FPG (central laboratory)  $\geq 13.3$  mmol/L
2. Week 12–before Week 24: venous FPG (central laboratory)  $\geq 11.1$  mmol/L
3. Week 24–Week 52: venous FPG (central laboratory)  $\geq 11.1$  mmol/L.

If a subject is confirmed to withdraw from the study due to hyperglycemia, the subject must complete termination visit before withdrawal (refer to Section 4.6). Then, the study medications can be discontinued and routine diagnosis and treatment can be started.

The Investigator must ensure no other causes can be identified to explain poor glycemic control except for lack of efficacy (e.g., acute inflammations/infections, concomitant treatments, etc.). If the disease aggravation is unexpected progression, it should be reported as an AE.

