## 9. Statistical Analysis

### 9.1 Sample Size Determination

This study plans to recruit 450 subjects. Considering possible drop-out of the subjects, a 20% increase of the total subjects, but no more than 564 subjects, will be enrolled. These subjects will be randomized at a ratio of 2:1 into HMS5552 treatment group or control group (placebo), i.e. no more than 376 subjects and 188 subjects are randomized to HMS5552 treatment group and control group.

Based on the planned sample size in efficacy analysis and the randomization ratio (450 subjects, HMS5552 treatment group: control group = 2:1), the study has 91.4% power to detect HMS5552 is superior to the placebo with 0.4% treatment difference (change of HbA1c from baseline at Week 24) under the assumption of type I error (alpha) at 0.05 (two sided) level and within-group standard deviation (SD) for the primary efficacy endpoint as 1.2%.

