## 5.3. Multiplicity

There's one primary efficacy endpoint and only one statistical analysis (Week 24). Efficacy endpoints in open-label treatment period (Week 52) will be analyzed with descriptive statistics. Thus no type I error rate ( $\alpha$ ) adjustment will be applied.

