## 9. Secondary Statistical Analyses

### 9.1. Secondary Efficacy Analyses

Secondary efficacy analyses will be conducted in FAS and PPS.

The secondary efficacy endpoints include changes from baseline at each visit (except Week 24) of HbA1c, and changes from baseline at each visit of FPG, 0.5h PPG, 2h PPG, Fasting C-Peptide, 0.5-hour postprandial C-Peptide, 2-hour postprandial C-Peptide, Fasting Insulin, 0.5-hour postprandial Insulin, 2-hour postprandial Insulin. The same analysis method for the primary efficacy endpoint is used, i.e. MMRM.

HbA1c response rate and composite HbA1c response rate will be calculated on basis of data imputed using LOCF method. Odds ratio (OR) and its 95% CI between two treatment groups will be estimated using logistic regression method.

Other secondary endpoints, such as HOMA- $\beta$ , HOMA-IR, HOMA2- $\beta$ , HOMA2-IR, I0/G0,  $\Delta$  I30/  $\Delta$  G30,  $\Delta$  C30/  $\Delta$  G30,  $\Delta$  I120/  $\Delta$  G120 and change from baseline in DI will be analyzed and compared using covariance analysis model for each treatment group. Calculation will be based on data imputed by LOCF.

The value and change from baseline of HbA1c, fasting plasma glucose and 2-hour postprandial plasma glucose from the end of double-blind treatment period (Week 24) to the end of study (Week 52) will be summarized with descriptive statistics by group. One of the groups consists of subjects who were randomized into HMS5552 treatment group. Another group consists of subjects who were randomized into placebo group and then switch to HMMS5552 treatment in open-label treatment period. Data at the end of double-blind treatment period (Week 24) will be set as baseline to summarize the value and change from baseline at each visit in open-label treatment period.

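### Open-label HbA1c, FPG and 2h-PPG are described to Week 52 in the subjects who remain after hyperglycemia withdrawals, so the visit means understate any loss of effect

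*Supplement*

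**What the plan says.** **Exit rule.** Protocol v1.1 Section 4.5.2 sets FPG limits by period; the last begins "Week 24–Week 52: venous FPG (central laboratory" and is 11.1 mmol/L or more. It must be met twice, at two consecutive visits, with no apparent cause. The investigator then evaluates whether the subject withdraws. Section 4.4.2 says that a subject who meets the criterion will be discontinued. A termination visit with the Visit 15 assessments, which include HbA1c, must come before a withdrawal for hyperglycemia.

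**Display.** SAP 9.1 states that HbA1c, FPG and 2h-PPG from Week 24 "to the end of study (Week 52) will be summarized with descriptive statistics by group". Both the value and the change from Week 24 are shown at each open-label visit. SAP 5.3 repeats the principle: "Efficacy endpoints in open-label treatment period (Week 52) will be analyzed with descriptive statistics". SAP 6.3 also calls for the pre-treatment value as a second baseline for the whole study.

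**Missing values.** SAP 6.1 states LOCF for the ANCOVA, and SAP 9.1.2 and 9.1.3 state it for the Week 24 response rates. The MMRM in SAP 8.1 compares HMS5552 with placebo to Week 24. SAP 6.6 maps a leaver's last visit to the nearest scheduled visit only if the gap and the time off drug are each at most 7 days. SAP 6.7 sets values after other antidiabetic drugs to missing.

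**The concern.** Exit depends on the quantity being displayed. Take a subject whose FPG is over the limit at Weeks 34 and 40 and who is withdrawn. This subject counts in the means at Weeks 24 to 40 but not at Weeks 46 and 52. After Week 28 the visits are six weeks apart, so the 7-day mapping cannot carry the exit value forward to the next visit. Each later mean is thus taken over a group from which the worst controlled have been removed, while the Week 24 mean still includes them.

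At stake is how the Week 52 table reads. SAP 2.2.2.2 lists Week 52 among the secondary endpoint times, and a reader will use the row of visit means to judge whether the effect lasts. A rise in HbA1c would look smaller than it is.

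**Working it through.** **1. The plan's own figure.** Protocol 9.1 gives "450 subjects, HMS5552 treatment group: control group = 2:1", "within-group standard deviation (SD) for the primary efficacy endpoint as 1.2" (percent) and "type I error (alpha) at 0.05 (two sided) level", and states that "the study has 91.4% power to detect HMS5552 is superior to the placebo with 0.4% treatment difference". The standard error is 1.2 × √(1/300 + 1/150) = 1.2 × 0.10 = 0.12, and 0.4/0.12 = 3.33. The normal approximation gives Φ(3.33 − 1.96) = 91.5%; the noncentral t with 448 degrees of freedom gives 91.4%. The figure reproduces, but it concerns Week 24 only. The dropout allowance ("a 20% increase of the total subjects, but no more than 564 subjects, will be enrolled") covers all causes. No document gives an open-label or hyperglycemia withdrawal rate, so everything below rests on assumed inputs.

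**2. Where the bias enters.** Let w be the share missing at Week 52 because of this rule. Then:

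- hidden in the visit means = w × (leavers' minus stayers' Week 52 level)
- hidden in the paired change from Week 24 = w × D, where D is the leavers' minus stayers' change
- the difference between the two = w × (leavers' minus stayers' Week 24 level)

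Leavers are likely to be well above stayers already at Week 24, so the visit means suffer more than the paired change. The change from the double-blind baseline has the same difficulty when Week 52 is read against Week 24, because the two figures cover different subjects.

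**3. Simulation A.** Assumed: Week 24 HbA1c 7.4% (SD 1.0), FPG 8.3 mmol/L (SD 1.9), correlation 0.7, HbA1c drift +0.30 points over 28 weeks (SD 0.6), rule always applied.

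| Quantity | HbA1c rise, Week 24 to 52 |
|---|---|
| True | 0.30 |
| Difference of visit means | 0.20 |
| Paired change in those remaining | 0.28 |
| MMRM | 0.29 |

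Seven percent are withdrawn. Taking all of them as missing at Week 52, the level gap is 0.10/0.07 = 1.43 points. Of this, 0.02/0.07 = 0.29 is a difference in change and 0.08/0.07 = 1.14 was present at Week 24.

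- Other inputs of this kind: 4 to 10% withdrawn, 16 to 42% of the visit-mean rise hidden, 4 to 11% of the paired change hidden.
- With assumed FPG drift and measurement noise added: visit-mean rise 0.06 to 0.23 (hidden 0.24/0.30 = 80% down to 0.07/0.30 = 23%), paired change 0.26 to 0.29, MMRM 0.29 to 0.30.
- With the rule applied to only half of those who meet it: about 6% missing, visit-mean rise 0.22, so 0.08/0.30 = 27% hidden.

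Together these give roughly 15 to 80% for the visit means and about 4 to 12% for the paired change.

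**4. A harsher test of the paired change.** Simulation B ties HbA1c change directly to FPG drift: 0.5 points per mmol/L, FPG 8.5 or 9.0 (SD 1.5), drift SD 1.5, half or all of those triggered withdrawn. With a true rise of 0.50, those remaining show 0.40 to 0.45, with 9 to 21% withdrawn. With a true rise of 0.25 they show 0.17 to 0.21. The hidden amount is 0.04 to 0.10 points, or 9 to 33% of the rise. So 4 to 12% is not an upper bound if failure of FPG and rise of HbA1c move closely together.

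**5. Without simulation.** For w from 2 to 15% and D from 0.5 to 2.0 points, w × D runs from 0.02 × 0.5 = 0.01 to 0.15 × 2.0 = 0.30; at 10% and 1.0 it is 0.10.

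**The case against.** Much of the other side stands.

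- **Paired change.** SAP 9.1 prints the change from Week 24, and SAP 6.3 makes it missing if either value is missing. That column already compares the same subjects. A reader might infer that a third of any loss is hidden from the report; that figure comes only from subtracting visit means with different denominators. In simulation A the MMRM improves on the paired change by just 0.01 points.
- **Other displays.** A reader might infer that failures vanish. SAP 9.2.8 plans a Kaplan-Meier plot of time to hyperglycemia withdrawal, SAP 7.1 tabulates withdrawal reasons over the whole treatment period, and SAP Table 2 gives the non-missing n. These show that subjects leave. They do not correct the means, and SAP 9.2.8 does not say that the curve runs to Week 52.
- **Automatic withdrawal.** Section 4.5.2 does not support this reading; it leaves the decision to the investigator. Discretion shrinks the bias without reversing it. Section 4.4.2 reads differently.
- **Late triggers.** A subject who first completes the criterion at Weeks 46 and 52 still has a Week 52 value, and exit values within the 7-day limits are used.
- **Purpose.** The open-label part is titled a safety evaluation and its efficacy is descriptive. That limits the weight of the point, but Week 52 is still a listed secondary time.

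**Conclusion.** The concern holds in a limited form. The visit means, and the change from the double-blind baseline when followed over time, compare different subjects and understate any loss of effect. The direction follows from an exit rule based on high FPG, provided leavers have the higher HbA1c. The size cannot be fixed from the documents: under the inputs of simulation A and its variants, roughly 15 to 80% of the rise in visit means and about 4 to 12% of the paired change. Under the closer FPG–HbA1c link of simulation B the paired loss is 0.04 to 0.10 points.

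The claim is clearest for the HMS5552-HMS5552 group. A reader might extend it equally to the Placebo-HMS5552 group, but those subjects start active drug at Week 24. Their column shows a response to starting treatment, and the upward drift assumed here does not describe them.

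Nothing here touches the Week 24 primary comparison.

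**What to change.** In SAP 9.1:

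1. Beside the observed-case table, add an MMRM of HbA1c and of FPG within each randomized group, in all subjects who received open-label HMS5552. Use Week 24 as baseline, enter termination-visit values under SAP 6.6, and give LS means with 95% CI at Weeks 28 to 52.
2. Beside each visit mean, including 2h-PPG, show the Week 24 mean of the same subjects and the cumulative number withdrawn for hyperglycemia.
3. State in SAP 9.2.8 that the Kaplan-Meier curve runs to Week 52.

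Separately, reconcile protocol Sections 4.4.2 and 4.5.2 on what follows when the criterion is met. No change of threshold or clinical rule is implied.

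The model adapts the code in SAP 8.1 and needs no new data. It assumes that, given the values already observed, those who left would have continued as similar subjects who stayed. The cost is a few extra tables and Week 52 figures that may look slightly less favourable.

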#### 4.5.3 Withdrawal due to Abnormal Liver Function

Depending on the subject's condition, study treatment can be discontinued if any of the following criteria is met (no need to wait for the retest results):

- ALT or AST  $> 8 \times \text{ULN}$
- ALT or AST  $> 5 \times \text{ULN}$  and lasts for  $\geq 14$  days
- ALT or AST  $> 3 \times \text{ULN}$  and TBiL  $> 2 \times \text{ULN}$
- ALT or AST  $> 3 \times \text{ULN}$  with liver damage symptoms (e.g., fatigue, nausea, vomiting, right upper abdominal pain or tenderness, fever, rash) or eosinophilia increase.

Active intervention or treatment needs to be given to subjects. The causes for abnormal liver function need to be identified. Consultation with hepatologists will be conducted if needed. Subjects with abnormal liver function are closely followed up until the liver function restore or the results return to baseline level. The termination visit should be scheduled as soon as possible within 3 days after discontinuation of study treatment. AEs relevant to abnormal liver function need to be recorded in time. SAEs which meet the criteria should be reported immediately.

